To examine the participants quality of life during the study period and at the time of relapse/progressive disease, patients in both arms will be asked to fill in the health-related quality of life (HRQoL) questionnaire every 2 months. The HRQoL questionnaires used are the EORTC QoL-30/LC13 and HADS questionnaire. EORTC-QoL-30 is a questionnaire containing 30 questions with five functional scales (physical function, role function, cognitive function, emotional function and social

function), three symptom scales (tiredness, nausea/vomiting, pain), a global health question and questions regarding frequent symptoms among cancer patients, such as dyspnea, sleep disturbances, loss of appetite, obstipation and diarrhea. The EORTC-QoL-30 also contains a question about financial difficulties. All scales will be linearly transferred to a score between 0-100. For functional scales and global health question, a score of 100 represents the best possible function, while a score of 100 on a symptom scale represents the worst possible symptom. A change in the score by 10 or more is considered a clinically significant change²⁰. LC13 is a supplementary questionnaire to the QLQ-C30 and includes 13 lung cancer-specific questions.

The HADS (The hospital anxiety and depression scale) is a fourteen-item scale. Seven items relate to depression and seven to anxiety. The tool has been developed for detection of anxiety and depression in patients with physical health problems. All items are scored from 0-3 with a possible total score between 0 and 21 for anxiety and depression respectively⁸.

Bjelland et al²¹ identified, in a systematic review, a cut-off point of 8/21 for anxiety or depression. For anxiety, the specificity was 0.78 and the sensitivity 0.9. For depression a specificity of 0.79 and a sensitivity of 0.83 was determined.

The generic EQ-5D-5L⁷ questionnaire will be used to assess quality-adjusted life years (QALY) for a health economic evaluation (*see statistics for details*).

Study design

The study is a multicenter randomised phase III study. After signing informed consent, the patient will be randomized in 1:1 fashion, to the *standard of care arm*, with planned CT-scans according to a standard schedule and measurement of quality of life every 2 months, or to the *experimental arm*, adding weekly PRO monitoring and quality of life measurements to standard of care.

Study population

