Eligible are patients with stage III lung cancer where the treatment intention is palliative and stage IV lung cancer regardless of treatment intent, who have received first-line induction treatment and have stable disease or better response after induction therapy. Maintenance treatment of any kind is allowed during the study period. Patients will be stratified by centre, stage and by main histology; small-cell lung cancer vs. non-small cell lung cancer.

Inclusion Criteria

1. Patients with lung cancer (NSCLC or SCLC) with stage III treated with palliative intention, or stage IV, regardless of treatment intention.
2. 1st line induction treatment* started/completed prior to the current evaluating scan
3. Non-progressive** disease at first CT scan evaluating 1st line induction treatment

4. Diagnosis proved by cytology or histology
5. Age \geq 18 years
6. Performance status (PS) \leq 2
7. First evaluation CT scan performed within four weeks from enrolment
8. The patient has given his/her written informed consent before any specific procedure from protocol

** Induction treatment includes:*

- *Standard doublet chemotherapy*
- *Immunotherapy*
- *Targeted therapy*
- *Palliative radiotherapy*
- *Local treatment of oligometastatic disease, including surgery and stereotactic radiotherapy*
- *Any combination of the above-mentioned treatment modalities. Patients are eligible regardless of whether they at the time of inclusion continue maintenance treatment or not*

*** Patients with stable disease or better response, defined by the treating clinician, are eligible. Patients receiving immunotherapy are eligible if pseudoprogression is suspected based on clinical response and treatment is continued. Patients receiving 1st line "treatment beyond progression" are eligible*

Exclusion Criteria

1. No internet access
2. No E-boks access
3. No mobile phone
4. Persons deprived of liberty or under guardianship or curators
5. Dementia, mental alteration or psychiatric disease that can compromise informed consent from the patient and/or adherence to the protocol and the monitoring of the trial
6. Pregnant or breastfeeding women
7. Patient participating in another interventional study during the surveillance period. This is only relevant for studies that might interfere with the intervention. Participation in protocols related only to treatment will not preclude participation in the present study. Cases of doubt will be settled by the protocol committee.

Time of enrolment

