The study plan for the randomized clinical trial is outlined in Table I. In the standard arm, all patients will be followed with CT-scan with the standard of care intervals and asked to fill in the web-based HRQoL questionnaires every 2 months. In the experimental arm, patients will additionally be asked to fill in the web-based PRO questionnaire on a weekly basis. If a detrimental change (See appendix) is noted in the patient's weekly responses to the PRO questionnaire, the patient will be contacted by a study nurse for verification of symptoms. If the symptoms are verified, the patient will be treated by the clinical staff according to standard procedures. If progressive disease is suspected, the patient will have the CT scan rescheduled to as soon as possible. All CT-scans will be described and evaluated by standard practice. It will entirely be up to the treating physician to interpret the results of the CT scans and to define the time of progression as well as the following treatment.

Evaluation at screening, prior to inclusion

The objective of these evaluations is to identify patients, who meet the specified Inclusion- and exclusion criteria. The patient will be informed verbally and in writing. Only patients who have signed informed consent will be included. Following examination and data will be collected prior to inclusion:

- Histological or cytological verification of lung cancer
- Disease stage at treatment start
- Prior treatment and/or maintenance treatment

- Baseline CT scan of the thorax and upper abdomen, showing no signs of progression, after completion of the first treatment for lung cancer, performed within 28 days of randomization.
- Baseline performance status (according to the ECOG's scale¹³), estimated within 14 days of randomization

The patient will be asked to fill in baseline health-related quality of life (EORTC QoL-30/LC13, HADS, EQ-5D-5L) questionnaires via E-Boks immediately after inclusion and then every 2 months.

Additional evaluation for the intervention arm, after inclusion

- Weekly response to the PRO application
- If detrimental changes in PRO responses, earlier evaluation, described above

CT evaluation according to standard follow-up/response evaluation, all participants

- CT-scan of the thorax and upper abdomen, to evaluate the time of progression (or relapse)

Evaluation at relapse or progression

- CT-scan of the thorax and upper abdomen
- Performance status
- Planned 2nd line treatment

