Generalizability of any study finding is important when considering future implementation processes. Previous trials of behavioural interventions among cancer patients have found that patients who choose not to participate have lower education and income, are more often single and have lower survival compared to participants²³⁻²⁵. In another parallel study, we will use registry data and baseline health-related quality of life to compare differences between participants versus non-participant. The aim is to assess differences in their lung cancer disease, symptom- and comorbidity burden, and socioeconomic characteristic. By understanding these differences, we hope to be able to improve future planning of PRO use in lung cancer follow-up for all patients (See appendix for details, sub-study 2).

Intervention costs, and the derived hospital resource use and costs (number of contacts, visits, scans etc.) can be used to estimate the difference in costs in the two arms. Data will be collected retrospectively upon completion of the trial (see Appendix, sub-study 3). Together with information on effects regarding the other endpoints (including health-related quality of life), this can provide a basis for a health economic evaluation of the intervention.

Data collection and analysis

Baseline information on age, gender, Charlson's comorbidity index (extracted from central registry), histology (extracted from the pathology database), TNM stage and treatment type will be noted. During the study period, the number of CT scans will be recorded, as well as disease status and deaths including the cause of death. After verification of progressive disease, the following cancer treatment modalities will be registered. Data will be filed in and stored electronically using the AmbuFlex system and transferred to REDCap (Research Electronic Data Capture) for further data management.

Data on resource use and costs for the health economic evaluation will be collected as a retrospective study upon completion of the trial, using 1) expert assessment for time and material spent on the intervention and 2) individual patient cost data

extracted from the National Patient Registry linked to the National Cost Database (See appendix).

Power calculation

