In the randomised study by Denis et al.² the difference in 1-year survival in control vs. PRO arm was 49% vs. 75% with the significant hazard ratio of 0.33 in their sample of 60 vs. 61 individuals in the two study arms. A power calculation based on a log-rank test for difference in survival with these anticipated survival rates and a follow-up time of 1-year results in for 53 patients in each arm. Given the remarkable difference between the two arms, a more conservative estimate has been calculated for a relative improvement of approximately half this size.

The crude overall 1-year survival in Denmark of 46.2%⁹, but given that patients included in the study are responders of initiated treatment and presumably have better survival, 50 % 1-year overall survival is assumed to be the survival rate in the control arm. A relative improvement of approximately half the size found by Denis et al.² would result in an anticipated survival rate of 63.2%. A difference of this size would require 221 individuals in each group (Alpha 5%, Beta-1 80%).

However, the feasibility study revealed a compliance ratio of 90%, which then requires a total number of 492 patients.

Power calculations were performed in STATA 14.2 using the procedure for two sample survival comparison with the log-rank test.

We aim to collaborate across hospitals to get as many participants as quickly as possible.

Statistics

The study will be conducted as a randomized phase III study. A temporary analysis will be made after 2 years of inclusion and determine whether the study holds enough promise to justify the continuation of patient enrollment. No predefined criteria for termination of the trial have been determined.

Cox proportional hazards regression will be used to estimate the hazard ratios for time to clinical deterioration, time or relapse, and the median time to deterioration.

OS will be compared between the control arms among all randomized subjects using a two-sided, log-rank test. Median OS will be estimated via the Kaplan-Meier method.

Health resources utilized are described in both arms. All hospital costs from the point in time from randomization to 1-year follow up are measured by DRGs (Diagnosis-related groups) and inflated to the price year 2018 using the Danish Hospital PL

(Price and Wage) index. CIs are estimated with bias-corrected non-parametric bootstrapping.

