Cost-effectiveness of the PRO application versus standard monitoring is assessed with the incremental cost-effectiveness ratio (ICER), i.e. the ratio of net health care costs to net QALYs (Quality Adjusted Life Years). For a description of the data collection and the analysis, see appendix.

Statistical analysis plan of the Health-Related Quality of Life data

Health-related quality of life (HRQoL) measures are secondary endpoints in the ProWide trial and will be reported in a scientific paper published separately from the main paper. The primary endpoints of the HRQoL paper are Physical function (QLQ-C30), Pain (QLQ C-30), HADS-anxiety and overall EQ-5D-5L index score.

The statistical analyses were planned before any evaluation of the data collected in the trial was made.

Data collection

The HRQoL questionnaires are sent to the patients via the Danish public mail system (eBoks) every second months. All patients in the trial have access to the system. Non-respondents receive a reminder after one week. Responses delivered > 30 days after the invitation is sent is categorized as “missing”.

Specific endpoints of interest in the HRQoL analysis

The specific HRQoL scales that will be analyzed in the ProWide study are:

1. Physical function (QLQ-C30)

Rationale: Physical function is considered a PRO surrogate marker for performance status which is an important prerequisite for both toleration effect of medical antineoplastic treatment.

2. Pain (QLQ C-30)

Rationale: Pain is sensitive to change toward progression in cancer and a symptom that can be managed with analgesics. The symptom could then be improved through actions that are a result of the intervention.

3. HADS-anxiety

Rationale: The intervention could improve the sense of security in the patients and potentially reduce anxiety.

4. EQ-5D-5L index score

Rationale: The generic score represents an overall self-assessed health status and will be used report the effect of the intervention on the overall health.

The EQ-5D-5L score will be reported both in the main paper as a mean-score comparison between the two groups at six months and also analyzed in the HRQoL paper as described below.

HRQoL hypothesis

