Health-related quality of life data based on the utility weights from the EQ-5D-5L questionnaires is collected as part of the trial at baseline and every second month. The EQ-5D-5L derived utility weights will be used to calculate the QALYs.

EQ 5D-5L is a generic questionnaire, consisting of five domains and a VAS scale and it is commonly used for estimating the generic health status, with high validity and reliability in various health conditions (3,4) and should be more sensitive at eliciting changes in the health status than the previous EQ-5D-3L questionnaire.

Analysis

Health resources used are described and compared for both arms (intervention and derived hospital costs) and are inflated to the price year 2018 using the Danish Hospital PL index (price and wage). Confidence intervals will be estimated using bias-corrected non-parametric bootstrapping.

In the five-year scenario, both costs and QALYs will be discounted to present value using an annual discount rate of 3%.

Furthermore, subgroup analysis will be undertaken to investigate explanatory factors for cost differences not related to the trial intervention. Finally, a number of sensitivity analyses will be run for the assessment of the robustness of the study assumptions.

Publications

The health economic evaluation will be described in a paper and submitted for a scientific journal in accordance with good reporting practice for health economic studies (4).

References

- 1) Drummond, M.; Schulper, MJ; Claxton, C; Stoddard, GL; Torrance GW.:
“Methods for the economic evaluation of health care programmes”. 4th Edition,
Oxford University Press, 2015
- 2) Herdman, M. et al. Development and preliminary testing of the new five-level
version of EQ5D (EQ5D-5L). Qual.Life.Res.20, 1727-36 (2011)
- 3) Janssen MF et al. Measurement properties of the EQ-5D-5L compared to the
EQ5D-3L across eight patient groups: a multi-country study. Qual.Life.Res. 22,
1717-27. (2013)
- 4) Husereau D; Drummond, M; Petrou, S; Carswell, C; Moher, D, Greenberg D;
Augustovski, F; Briggs AH; Mauskop J; Loder E. and on behalf of the
Consolidated Health Economic Evaluation, Reporting Standards (CHEERS)
statement CHEERS Task Force. Cost-effectiveness and Resource Allocation
2013, 11:6
Downloaded from <http://www.resource-allocation.com/content/11/1/6>

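### No covariate adjustment is specified for the cost and QALY differences behind the ICER, although treatment at entry and baseline EQ-5D-5L utility are recorded

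*Combined protocol and SAP*

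**What the plan says.** Cost-effectiveness is a listed secondary endpoint. The relevant text is spread over several sections of the combined protocol and SAP.

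- **Costs.** The Sub-studies section says that intervention costs and derived hospital costs "can be used to estimate the difference in costs in the two arms". The Statistics section and the Analysis part of Appendix sub-study 3 describe and compare resource use by arm, with bias-corrected non-parametric bootstrap intervals.
- **ICER.** The Statistics section defines it as "the ratio of net health care costs to net QALYs" and refers to the appendix for the analysis. The appendix names no model and no covariate.
- **QALYs.** Under Implementation of the intervention, the EQ-5D-5L "questionnaire will be used to assess quality-adjusted life years (QALY) for a health economic evaluation". Appendix sub-study 3 builds QALYs from the baseline and two-monthly utilities.
- **Other cost drivers.** Appendix sub-study 3 adds that "subgroup analysis will be undertaken to investigate explanatory factors for cost differences not related to the trial intervention", and plans sensitivity analyses whose content is not given.
- **What is recorded at entry.** The list under Evaluation at screening includes "Prior treatment and/or maintenance treatment". Data collection and analysis also lists treatment type, and Evaluation criteria places the EQ-5D-5L at baseline.
- **Stratification.** Study population: "Patients will be stratified by centre, stage and by main histology". Treatment type and utility are not among the factors.

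**The concern.** Patients enter after treatment has ended, on continuing systemic treatment of several kinds, or after local treatment only (Time of enrolment). That status is fixed before randomisation and plausibly bears on later hospital cost. The synopsis background itself says that scan intervals differ between maintenance treatment and follow-up, and by treatment type. Baseline utility enters the QALY directly and is likely to predict later utilities.

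A chance difference between arms in either variable therefore moves the net cost or the net QALYs, and so the ICER. The planned subgroup analysis shows that the authors expect cost differences unrelated to the intervention. A subgroup analysis, however, leaves the overall cost difference and the ICER as they were, and it does not touch QALYs. Because the economic evaluation follows trial completion, leaving adjustment open also means that covariates could be chosen after the results are known.

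**Working it through.** **The plan's own figure.** No precision figure is given for costs, QALYs or the ICER, so the survival sample size only supplies n. From Power calculation: 50% vs 63.2% 1-year survival, alpha 5%, power 80%, 221 per arm.

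- HR = ln(0.632)/ln(0.50) = 0.662.
- Freedman's formula gives 190 events. The mean event probability is 1 − (0.50 + 0.632)/2 = 0.434, so 190/0.434/2 = 219 per arm, within 3% of 221. A two-proportion formula (pooled, no continuity correction) gives exactly 221.
- 221/0.90 = 245.6, rounded up to 246 per arm, 492 in total. This agrees with the plan.

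**Treatment type at entry.** The share p is not in the documents; 20-50% is assumed. The 95% range of chance imbalance is 1.96 × √(2p(1−p)/246).

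| p | SE | 95% range |
|---|---|---|
| 0.20 | 0.0361 | ±7.1 points |
| 0.40 | 0.0442 | ±8.7 points |
| 0.50 | 0.0451 | ±8.8 points |

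If G is the yearly cost gap between those with and without that treatment type, net cost moves by ±0.07G to ±0.09G. G is not in the documents.

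**Precision of the cost difference.** The share of cost variance explained is R² = p(1−p)G²/(p(1−p)G² + s²), with s the within-group SD. Take p = 0.4.

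- G = s: R² = 0.24/1.24 = 0.19, and the interval is 1 − √0.81 = 10% narrower.
- G = 2s: R² = 0.96/1.96 = 0.49, and the interval is 1 − √0.51 = 29% narrower.

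**QALY gain implied by the plan.** With exponential survival, mean time alive in year 1 is (1 − 0.50)/0.693 = 0.721 vs (1 − 0.632)/0.459 = 0.802, a difference of 0.081 years. At an assumed mean utility of 0.70 to 0.75 this is 0.056 to 0.060 QALY.

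**Shift from baseline-utility imbalance.** Shift = 1.96 × SD × √(2/246) × slope × 0.762, where 0.762 is the mean of 0.721 and 0.802. The SDs and slopes on later utility are assumptions.

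| SD | Imbalance (95%) | QALY shift, slope 0.5 | QALY shift, slope 1.0 |
|---|---|---|---|
| 0.15 | ±0.027 | ±0.010 | ±0.020 |
| 0.20 | ±0.035 | ±0.013 | ±0.027 |
| 0.30 | ±0.053 | ±0.020 | ±0.040 |

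**Precision of the QALY difference.** Two simulations with 246 per arm and exponential survival:

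- Between-patient utility SD 0.15, 0.20, 0.25, mean utility 0.75, measurement SD 0.10 (3,000 trials): raw SE 0.0245, 0.0257, 0.0270; adjusted about 0.023. Variance falls by 10%, 18%, 27%. On the interval scale that is 1 − √0.90 = 5%, 1 − √0.82 = 9% and 1 − √0.73 = 15%.
- Utility SD 0.20, baseline-QALY correlation about 0.33 (4,000 trials): SE 0.0240 raw, 0.0227 adjusted, about 5% smaller. The average difference is 0.057 raw and 0.058 adjusted, so there is no bias. Where baseline utility favoured the intervention by more than 1 SE (0.018), the raw difference averaged 0.069; where it favoured control by as much, 0.044. The adjusted difference averaged 0.057 in both cases.

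**The case against.** A reader might infer that the plan has decided on raw arm differences. It has not said so. It is silent on adjustment, and Appendix sub-study 3 commits in general terms to recommended practice for economic evaluation. The accurate statement is that adjustment is not specified.

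A reader might also infer that the cost-effectiveness result will be biased, or that a baseline difference will be mistaken for an effect. That does not follow. Under randomisation the unadjusted differences are unbiased, and the bootstrap already carries chance imbalance. In the first simulation the 95% half-width for QALYs is about ±0.048 to ±0.053 unadjusted (1.96 × 0.0245 to 0.0270) and ±0.045 adjusted. The baseline-driven shift under the same inputs, ±0.016 to ±0.028, lies inside either.

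Nor do the documents support saying that treatment cost swamps the cost of the intervention. They give no cost gap, no share on costly drugs and no intervention cost. The Statistics section measures hospital costs by DRG, and how far drug cost enters at patient level is not described.

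Further limits stand. Stratification by centre, stage and histology reduces the treatment imbalance, and the gain from adjusting for it, to the extent that these factors predict treatment. The simulations have no progression step, while patients exit the study at progression. Nothing was calculated for the 5-year horizon.

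Adjustment also carries a risk of its own. Evaluation criteria puts the baseline EQ-5D-5L at randomisation; Evaluation at screening puts it immediately after inclusion, by E-Boks. The HRQoL plan accepts responses up to 30 days after the invitation. The value may therefore be given once the arm is known, and adjusting for such a value can introduce bias.

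What survives is an efficiency point: a better method is available from data already collected, and the planned subgroup analysis does not replace it.

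**Conclusion.** The point holds as an improvement to the analysis, not as an error that invalidates it. Without adjustment the estimates remain unbiased and the intervals valid, but those intervals are wider than the data require and the point estimate moves with chance imbalance.

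On the cost side the movement is 7-9% of the cost gap between treatment types (share 20-50%, assumed), and adjustment narrows the interval by about 10-29% if that gap is 1-2 within-group SDs (assumed). On the QALY side the movement is roughly ±0.01 to ±0.04 against an implied 1-year gain of about 0.06, and the interval narrows by about 5-15%. The survival rates and the 246 per arm come from the plan; utilities, SDs, slopes, shares and cost gap do not. The QALY adjustment is sound as the main analysis only if baseline utility precedes knowledge of the arm.

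**What to change.** In the Statistics section (ICER paragraph) and the Analysis part of Appendix sub-study 3, before cost and outcome data are linked:

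1. Estimate incremental cost from a regression on arm, treatment at entry (with a category for combinations of modalities) and the stratification factors: centre, stage and histology.
2. Estimate incremental QALYs from a regression on arm, baseline EQ-5D-5L utility and the same stratification factors.
3. Refit both regressions in every bootstrap replicate and build the ICER from the adjusted differences. Report the unadjusted results as a sensitivity analysis.
4. Keep the planned subgroup analysis of cost differences, labelled exploratory.
5. State a simple rule for a missing baseline utility, for example mean imputation of the covariate, so that no patient is dropped for lacking it.
6. Reconcile Evaluation criteria with Evaluation at screening so that the baseline EQ-5D-5L is completed before the arm is known. If it was not, make the QALY model without baseline utility the main one and show the version adjusted for it as a sensitivity analysis.

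The cost is SAP wording, a little more analysis work and two versions of the result to report. The covariates are already collected.

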Exclusion criteria	
 1. No internet access 2. No E-boks access 3. No mobile phone 4. Persons deprived of liberty or under guardianship or curators 5. Dementia, mental alteration or psychiatric disease that can compromise informed consent from the patient and / or adherence to the protocol and the monitoring of the trial 6. Pregnant or breastfeeding women 7. Patient participating in another interventional study during the surveillance period. This is only relevant for studies that might interfere with the intervention. Participation in protocols related only to treatment will not preclude participation in the present study. Cases of doubt will be settled by the protocol committee.
Time of Enrolment	Patient enrolment is always at the time when the patients are informed of the results of their first evaluation scan after treatment induction.
Statistical analysis	The study will be conducted as a randomized phase III study. First analyses will be conducted after 2 years of inclusion. No predefined criteria for termination of the trial has been determined.

Introduction

Lung cancer is a serious disease with a dismal prognosis. The 5-year survival rate of Danish lung cancer patients diagnosed with loco-regional disease ranges from 43% for patients with stage I lung cancer, through 27% for stage II to 21% for patients with stage III disease. Patients with stage IIIb-IV receiving palliative treatment have an even worse outcome, with a 5-year survival of only 4 and 2% estimated in 2015. Of the more than 4500 patients who were diagnosed with lung cancer in Denmark in 2015, 55.6% were in stage IIIb-IV⁹.

According to the national Danish follow-up program for lung cancer, patients are followed with clinical controls and a contrast enhanced CT-scan of the thorax and upper abdomen, every 3 months the first 2-3 years, then every 6 months until 5 years. The purpose of follow-up is to find relapse as soon as possible to increase the probability of curative treatment of the relapse, or if curative treatment is not possible, optimal palliative treatment¹. In case of treatment with palliative intent, patients are usually scanned every 3 months after they have finished treatment to determine the present status of the disease. However, during palliative treatment, patients are often scanned more frequently to evaluate the effect of the ongoing treatment.

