- Categorization of the performed CT scan as prescheduled as a result of a PRO notification

Study period:

Patients will be followed for two years after inclusion in case of non-progressive disease. In case of progressive disease or relapse, the patient will exit the study. For survival analysis and further evaluation, patients will be followed until death or up to 5 years from inclusion.

Endpoints:

The primary outcome measures that will be compared between the experimental and control arm is overall survival with an observation time of 24 months.

The secondary outcome measures are

- Performance status at the time of progressive disease
- Progression-free survival
- Health-related quality of life
- Cost-effectiveness and hospital resource use and costs
- Type of treatment at the time of progressive disease

Time to progression as well as performance status at progression compared to performance status at enrolment into the study may be used to investigate, whether the intervention leads to earlier detection of and better performance status at the time of progression. Quality of life differences may provide insights on possible other patient perceived benefits to the web-mediated follow-up.

Sub-studies

A parallel research project has been financed and will focus on benefit in terms of quality of life and better patient involvement through qualitative interviews with patients included in the study. With qualitative interviews, we aim to describe how participants experience the web-based PRO application and to explore the mechanisms of action related to PROs as a mean of patient involvement. Moreover, we aim at exploring how the intervention influences patients' fear of cancer recurrence and their psychosocial well-being. We will apply the method of an interpretive description as an inductive, flexible research strategy to generate knowledge relevant within a clinical context²². Individual semi-structured interviews will be conducted with 8-10 patients from each arm. After one year, follow-up interviews will be conducted with the same participants in order to explore transformations in the patients' experiences and give new insights in barriers and opportunities for patient involvement in follow up of lung cancer (For details, see appendix, sub-study 1).

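### Does the loosely described analysis after two years of recruitment threaten the overall survival result?

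*Combined protocol and SAP*

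**What the plan says.** The Statistics section schedules one analysis two years into recruitment. Its stated task is to "determine whether the study holds enough promise to justify the continuation of patient enrollment", and the next sentence reads "No predefined criteria for termination of the trial have been determined". The synopsis, under Statistical analysis, repeats the absence of criteria and describes the look more loosely: "First analyses will be conducted after 2 years of inclusion".

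The final comparison is given once: "OS will be compared between the control arms among all randomized subjects using a two-sided, log-rank test". (The reference to control arms is a slip for the two study arms.) The Power calculation section uses a fixed design with 5% alpha and 80% power, giving 221 per group, raised to 492 in total for 90% compliance.

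Four other sections bear on the point:
- Endpoints: the primary outcome "is overall survival with an observation time of 24 months".
- Study period: "For survival analysis and further evaluation, patients will be followed until death or up to 5 years from inclusion".
- Timetable: recruitment starts in September 2018, preliminary findings are analysed in July–December 2020, and the final paper, with every patient followed for 24 months, is expected in the second half of 2022.
- Publications: the study is reported once it is complete and the final analyses are done.

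**The concern.** An analysis that can change the course of a trial normally comes with an endpoint, a list of permitted decisions and a statement on alpha. Here all three are absent, beside a sample size that allows for a single test. OS is the only primary endpoint, so a comparison of OS by arm is a natural, though inferred, reading of what would be examined. The text also moves within two sentences from continuing enrolment to terminating the trial.

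Two uses would do harm. If OS could be declared significant at 0.05 at the look and again at the end, the false-positive rate would exceed 5%. If the trial ended at the look and OS were tested on the deaths then available, power could fall below plan. Without a written rule, a reader of the final paper might be unsure which use applied.

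**Working it through.** **Inputs.** One-year survival 50% and 63.2%, 5% alpha, 80% power, 221 per group and 492 in total (Power calculation); 1:1 allocation (Study design); 24-month observation (Endpoints); dates (Timetable). Assumed: exponential survival, proportional hazards, and accrual either uniform or staggered by site opening with equal site rates (opening at months 0, 2.5, 2.5, 4, 6, 6, 11 and 11).

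**The plan's sample size.** HR = ln 0.632 / ln 0.5 = 0.662. Freedman's formula gives 190 deaths; 190 / 0.434 (mean one-year death rate) = 438, or 219 per group. The two-proportion formula gives exactly 221. Then 221 / 0.9 = 245.6, so 246 per group and 492 in total. The plan's figure is reproduced with no interim adjustment.

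**Deaths at the final analysis.** Within 24 months: 246 × [(1 − 0.5²) + (1 − 0.632²)] = 246 × (0.750 + 0.601) = 332 under the planned effect, and 492 × 0.75 = 369 under no effect. Power = Φ(|ln HR| × √(deaths/4) − 1.96) = Φ(0.4125 × √83.06 − 1.96) = Φ(1.80) = 96%. This exceeds 80% because it counts deaths to 24 months in all 492 patients; the plan's 80% counts one year in 442.

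**When enrolment would close.** Full 24-month follow-up by the end of 2022 requires the last patient by December 2020, month 27. The look falls at month 24. If enrolment has closed by then, the decision has no effect.

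**Written use: the look decides on enrolment only, follow-up continues, one final test at 0.05.** Month-27 close, simulated; ranges cover the two accrual patterns.

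| Enrolment ends at the look if | Type I error | Power |
|---|---|---|
| two-sided p < 0.05 | 5.2% | 96.1% |
| unfavourable trend | 5.0% | 96.3–96.4% |
| two-sided p ≥ 0.05 | 4.7–4.8% | 94.0–94.6% |
| always | 5.0% (ignores the data) | 93.7–94.3% |

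The last row has 286–295 deaths; for uniform accrual, 332 × 24/27 = 295.

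**Longer accrual.** If enrolment always ends at month 24 and would have taken A months at a uniform rate, deaths = 332 × 24/A:
- A = 30: 266 deaths, Φ(1.40) = 92%.
- A = 36: 221 deaths, Φ(1.11) = 87%.
- A = 48: 166 deaths, Φ(0.70) = 76%.

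Ending enrolment on a favourable result (Z > 1.645 or Z > 1.96) gives a type I error of 5.2–5.4% when the look holds 0.5 or 0.4 of the information and enrolment is 80% or 67% complete, which is close to 30- and 36-month accrual.

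**Uses not written.**
- OS declarable at 0.05 at both times: with correlation √t between the two statistics, the two-sided error is 7.7% at information fraction t = 0.66, 8.0% at 0.60, 8.2% at 0.53 and 8.5% at 0.44. With accrual as long as 48 months (t about 0.31) it is 8.9%.
- Trial ended and tested at the look: 146–214 deaths, power 70–86%. The planned 80% needs about 185–190 deaths, so this range straddles the plan's own target.

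**The case for a change.** The strongest reply is that nothing expressly bars an efficacy claim at the look. The synopsis does not tie the look to enrolment, preliminary findings are due for analysis at about the same date, and if enrolment is nearly complete by then, an enrolment decision has little left to decide. The look might then serve mainly as an extra view of OS. Nor is it labelled a futility analysis. If a stop for lack of promise were simply counted as a negative trial, power at the planned effect would be 90–95% with a cut at Z < 1 and 80–91% with a cut at Z < 1.5 (information fractions 0.4–0.6), though type I error would then fall.

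The gap in the text is real, and that part stands. The harmful readings do not. The primary outcome needs 24 months of observation, and at month 24 of recruitment almost no patient has it. Survival follow-up continues after a patient leaves the study at progression, the final paper is tied to complete 24-month data, and publication waits for the final analyses. The timetable entry on preliminary findings does not mention OS by arm. Saying twice that there are no termination criteria fits a trial with no planned early stop at least as well as one with an open-ended stop.

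Two limits on the reassurance also stand. The 2–3 point power cost depends on enrolment closing by month 27, and the Timetable also lets enrolment run until the target is met. But 36-month accrual would put the last 24-month visit in September 2023 and 48-month accrual in September 2024, both beyond the planned final paper. And writing down a rule would not by itself recover the power lost by ending enrolment early.

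**Conclusion.** No change to the plan follows. The description of the look is thin, but a trial statistician would fill the gap from the surrounding sections: the look informs enrolment, survival follow-up goes on, and OS is tested once, at two-sided 0.05, with 24-month data. On that reading type I error is 4.7–5.2% and power is 94–96%, given a close by month 27. With 36-month accrual, ending enrolment at the look would still leave about 87%; only at about 48 months would it fall below the planned 80%, to 76%.

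The 8% error and the 70–86% power belong to uses that no section describes. A formal boundary such as Haybittle-Peto (p < 0.001 at the look) would hold overall error at 5.01–5.03%, but it would give the trial an efficacy stop it does not have. Restricting the look to pooled data would remove the purpose it was given. Neither improves the final test.

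The conclusion rests on exponential survival at the protocol's one-year rates, proportional hazards, the assumed accrual patterns, and the reading of the Endpoints, Study period, Timetable and Publications sections as pointing to a single final OS analysis. It would change if OS were in fact declared significant at the look.
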